PHIT interventions targets improvements in physical function in a real world home setting. This paradigm-shifting proposal carries low risk to patients because the exercises are supervised by licensed professionals and tailored to the home environment of each person. All testing occurs at home rather than a laboratory setting to increase generalizability and minimize participant burden. Furthermore, the proposed intervention is designed to demonstrate that even in isolated treatment environments (e.g., home setting), more intensive treatments can be safely and effectively implemented. Such evidence will help counter perceptions that conservative intervention approaches are safer in isolated home treatment settings. Updating practices for older Veterans with hospital-associated deconditioning is a VHA Priority: Our proposal is strongly aligned with the goals outlined in the Veteran's Health Administration (VHA) Office of Geriatrics and Extended Care (GEC) strategic plan,³⁸ specifically goal 1: Commit to Veteran-centric care, and goal 4: Continuously improve geriatric care through ageappropriate performance indices.

Goal 1: Commit to Veteran-Centric Care

The VHA GEC has proposed a stronger focus on Veteran-centric care, which includes a focus on outcomes important to the Veteran population. Older Veterans have identified many barriers limiting their community mobility after hospital discharge; however, no protocols have been established to prioritize a return to community mobility in this population. Our PHIT intervention will examine how physical therapy influences the changes in life-space mobility after hospitalization, and how these changes are related to therapy dose.

Goal 4: Continuously Improve Geriatric Care through Age-Appropriate Performance Indices

This goal strives to identify and establish benchmarks of physical function in transitionally frail older Veterans. By targeting Veterans with deconditioning after an acute hospitalization, we can start examine what functional measures are biomarkers for adverse health event risk and determine which are most responsive to PHIT interventions. This will help establish functional benchmarks in the older Veteran population, and may contribute to additional care process measures in HBPC to identify and intervene upon these deficits.

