| Heart Disease Spinal Stenosis A fibrillation Post-op bowel surgery | surgery Hypercholesterolemia Dehydration Hypo/Hyperthyroid Congestive Heart Failure | Peripheral Arterial Syncope Renal Failure-no dialysis |

The diagnoses most commonly reported for home health patients are diabetes, hypertension, heart failure, chronic ulcerative wounds, and osteoarthritis.

5. Be ambulatory without human assistance prior to hospitalization and be able to maintain a gait speed between 0.3 m/s-1.0 m/s at baseline assessment. Gait speed test may be administered in hospital to determine study eligibility.

Inclusion Criteria for Caregivers:

• Primary caregiver for an enrolled participant in the study

Exclusion Criteria for Veterans/spouse of Veteran (one or more):

- 1. Acute lower extremity fracture with weight-bearing restriction
- 2. Elective joint replacement surgery

- 3. Lower extremity amputation
- 4. Acute cardiac surgery
- 5. Terminal illness or end stage kidney disease requiring dialysis
- 6. Alzheimer's Disease
- 7. Deep vein thrombosis/pulmonary embolus VT/PE
- 8. Recent stroke
- 9. Progressive neurodegenerative diagnosis (e.g. Parkinson's, MS, ALS)
- 10. Active involvement of Adult Protective Services
- 11. Active cancer treatment in which exercise is contraindicated
- 12. Currently enrolled in home health physical therapy upon admission to VAMC

13. Clinical discretion of study physician to exclude patients who are determined to be unsafe and/or inappropriate to participate in high intensity rehabilitation as defined by the inclusion/exclusion criteria

Additional exclusion assessed prior to randomization: the inability to ambulate ten feet with human assistance.

Exclusion Criteria for Caregivers:

• Being on probation or alternative prison sentencing.

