D2.5. Intervention: Patients in the PHIT exercise group will receive between 10 and 12 PT visits in their home (45-60 min/session). Data from 3 local home health agencies indicated that the average number of physical therapy visits per episode of care was 8.5 (Agency 1), 7.8 (Agency 2), and 8.6 (Agency 3). Furthermore, the average number of PT visits from the preliminary data for the PHIT and UC groups were 9.8 and 8.4 visits, respectively. Therefore, we chose to target 10-12 PT visits for the proposed study to operate within a reasonable range of the current standards of care and maximize the benefits of the PHIT intervention. Our preliminary data suggest that this frequency of visits (10-12 visits over 4 weeks) will produce neuromuscular and physiological changes that will translate to improved function. Patients in the PHIT group will receive 3-4 visits per week for the first two weeks and 2 visits per week, on non-consecutive days for the remaining 2 weeks (total=10-12 visits). The intervention will consist of progressive resistance exercises for the lower extremity with a portable training device (Shuttle Mini-Press), a motor control-based program of gait/balance training, and ADL training—all designed to

improve mobility (see Table 2; Appendix). PHIT participants will also receive specific written nutritional education to emphasize the importance of increasing protein intake by 15 grams/day to support participation in the high intensity program (see Appendix).

The patients in the UC group will also receive 10-12 visits to match the PHIT group over 4 weeks. We will provide a standardized rehabilitation protocol for the UC group to perform over the 10-visit intervention period, which consists of a controlled low intensity program with activities from each of the domains included in the PHIT program (see Appendix). Both groups will also receive a standardized simple home exercise program, which will include identical exercise activities that differ only on intensity (See Appendix).

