Progressive High Intensity Therapy: The strength component of the PHIT intervention will be performed using a portable progressive resistive exercise machine that uses latex bands providing 6 to 100 pounds resistance (Shuttle Mini Press, Contemporary Design Company, Glacier, WA). The use of the shuttle press allows for standardization of treatment intensity across therapists while ensuring appropriate overload for high intensity strength training. The use of the device will not limit generalizability of study results because a number of alternatives for lower extremity strengthening can be easily implemented in the home setting, and previous research has demonstrated equal benefits for strength training using exercise bands and formal free weights when performed at equivalent intensities.⁷³ The exercise intensity will be an 8repetition maximum, and the volume will be 3 sets of 8 repetitions. This protocol has been used safely and effectively in frail elders.^{74,75} For the first week, participants will perform 2 sets for 3 different exercises and will increase to 3 sets for the remainder of the program. Intensity will be re-evaluated weekly and resistance will be increased if the participant is able to complete 8 repetitions at the higher load using good movement form. Using the Shuttle Mini-Press will also allow us to estimate total training volume (weight lifted x repetitions) more precisely. We can then use total training volume as an explanatory variable in our analysis to determine if training volume explains additional variability in functional gains within the PHIT group-this will help provide additional evidence for efficacy of the PHIT program in deconditioned Veterans. We will not be collecting any data about the efficacy, feasibility, or safety of the Shuttle Press in promoting the strength gains specifically; we are simply using this device as one of many clinically appropriate modes of delivering exercise for this population (it is equivalent to using theraband, or free weights to deliver exercise). Thus, we do not consider use of the Shuttle Press as a medical device.

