The motor control system of PHIT mobility training begins with exercise tasks requiring low skill and progresses to more skilled movements as previously described.^{68,69} For example, the patient is instructed to step to a visual target placed in different positions. Stepping activities are performed repeatedly in one direction or to one side, then to the opposite side. As performance becomes skilled (i.e., accurate and smooth), then alternating stepping activities are attempted. Walking activities are also progressed from low skill (e.g., walking in a straight line) to more skilled activities such as walking in a serpentine pattern. Progression is based on increasing speed, accuracy, and finally with holding or manipulating of an object (dual task). Each session begins with practicing a "well-learned task." Patients are progressed when performance of the task is 80-100% correct. As walking ability improves, this training begins to target patient endurance by prescribing daily walking programs for two 10 minute bouts and increasing to 20 minutes continuous. Before discharge from home therapy, patients will begin to transition to an unsupervised physical activity program by performing a daily walking program and independent home exercises.

The **PHIT Activity of Daily Living (ADL) training** focuses on increasing mobility in activities needed in daily life. Training in ADLs emphasizes safety and compensation strategies to

maximize independence. Activities include bathroom transfers, bed mobility (e.g. rolling, supine \rightarrow sit), and car transfers. These activities will be delivered at higher intensities than UC as described above in section D.1.2.

Nutritional Education Specific to PHIT Program: While all Veteran participants will receive nutrition screening and education at baseline, those randomized to the PHIT group will have ongoing nutritional education from the interdisciplinary team and be encouraged to supplement protein intake by at least 15g/daily to support participation in higher intensity exercise strategies.^{76,77} Written education about what foods contain at least 15g of protein will be provided to all PHIT group participants. Along with the rest of the interdisciplinary team, physical therapists will follow up on this education and document compliance each visit (see Appendix).

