A manual will be provided to each clinician with protocol details, clinic and home exercise pictures, documentation forms, and study contact information. Research Physical Therapists will review the intervention data sheets biweekly, and will conduct monthly phone meetings with the PHIT and UC physical therapists. If the treatment fidelity is below 90%, additional training sessions will be scheduled with individual therapists. Treatment fidelity data will provide information on the adherence of the PT to the interventions, the adherence of the participants to the prescribed activities, and will provide an opportunity to address potential study problems (see Appendix). In addition, every month for the first year, and every three months thereafter, treating therapists will meet to discuss treatment guidelines and any issues that have surfaced. For each agency therapist, the research physical therapists will observe 4-5 home sessions for the first 2 patients. These on-site observations may be supplemented with video conferencing during treatment sessions for additional oversight as necessary. Should new therapists require training during the course of the investigation, the same procedures for initial training and monitoring will be implemented. Each treating therapist will fax documentation weekly to ensure protocols are being followed.

Blinding of Research Staff: Only the research physical therapists conducting staff training, and the VNA HH or Berkley Home Health agency manager will have full knowledge of group assignment. Outcome data will be assessed by Physical Therapist Outcomes Assessors who will remain blinded to treatment group. Intervention PTs will only provide either PHIT or UC intervention. Patients will be instructed not to discuss what they do during their home physical therapy sessions with the Physical Therapist Outcomes Assessor to maintain blinding, and also be asked to not share the group assignments during any care coordination meetings.

C. Description, Risks and Justification of Procedures and Data Collection Tools:

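### Assessor blinding is vulnerable: outcomes are tested in the home where treatment was given, and no safeguard covers arm-specific material that may be visible there

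*Combined protocol and SAP*

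**What the plan says.** - **Place of testing.** Section II (paragraph on the real-world home setting): "All testing occurs at home rather than a laboratory setting". The one exception concerns eligibility (Section IV.B, inclusion criterion 5): "Gait speed test may be administered in hospital to determine study eligibility".
- **Masking.** D2.1 calls the trial single blind. The section Blinding of Research Staff names the outcomes assessors as the blinded party.
- **What differs by arm in the home (D2.5, Table 2).** PHIT strength training uses "a portable progressive resistive exercise machine that uses latex bands"; Table 2 lists the Shuttle Mini-Press for PHIT only. On nutrition: "Written education about what foods contain at least 15g of protein will be provided to all PHIT group participants". Both arms receive a home exercise program, "which will include identical exercise activities that differ only on intensity".
- **Safeguards.** Blinding of Research Staff limits full knowledge of allocation to the research physical therapists who train staff and the agency manager, uses separate assessors, and has each treating therapist deliver one arm. It adds: "Patients will be instructed not to discuss what they do during their home physical therapy sessions". Participants are also asked not to share their assignment in care coordination meetings. D2.3 tells therapists not to reveal their protocol to other therapists.
- **Primary outcome.** Self-selected gait speed at day 60 (Sections IV.A and F), with statistical significance resting on one test.

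**The concern.** Participants and treating therapists know what exercise is being done, so the protection of the outcome measurements lies with the assessor. Self-selected gait speed is timed by a person who gives the instruction, and an assessor who believes the participant had the intensive program could, without intending it, prompt or time differently. Any such bias would most plausibly favor PHIT. The same holds for the SPPB, mPPT, TUG and dynamometry.

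The safeguards all act on information passing between people. An assessor who walks into the room where treatment took place may learn the arm from objects instead, and nothing in the plan addresses that route or would reveal afterwards whether it had been used.

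**Working it through.** **1. What each safeguard controls**

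| Safeguard | Controls | Covers objects in the home? |
|---|---|---|
| Full knowledge of allocation limited to named roles | Who is told | No |
| Separate blinded assessors | Who is told | No |
| Each therapist delivers one arm | Mixing of protocols between arms | No |
| Therapists do not reveal their protocol to other therapists (D2.3) | Speech | No |
| Participants do not discuss sessions or share assignment | Speech | No |

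The documents also contain no assessor guess, unmasking record or other check.

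**2. Which cues could be present, and when**

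- The program is "10-12 visits over 4 weeks", so it ends about 30 days before the day-60 test. The press is portable, and nothing says it is left behind. Paper handouts can remain.
- There is also an assessment at day 30 (D2.1, Table 1). In the pilot, treatment ended on average at 31.1 days (PHIT) and 35.3 days (UC) (Figure 2 caption), so therapy may still be under way at that visit. Nothing requires a different assessor at day 60, so an inference made at day 30 could carry forward.

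**3. Two passages that add to the risk**

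- Section IV.A: at each of the five study visits the adverse-event script asks about adherence to exercises. The answer could disclose the very content that participants are told not to discuss. The documents do not say who administers the script or at what point in the visit.
- Section IV.C has standing and walking tests supervised by either a PRA or a research physical therapist. Blinding of Research Staff gives the research physical therapists who train staff full knowledge of allocation. D2.3 describes the assessor as a physical therapist or trained research assistant, while Blinding of Research Staff mentions only physical therapists. The three passages do not fit together as written.

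**4. The plan's own sample-size figure**

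Inputs (Sample Size Estimates): difference 0.18 m/s, SD 0.29 m/s, two-sided alpha 0.05, 56 completers per group, 90% power.

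- Normal approximation: n = 2 × (1.960 + 1.282)² × 0.29² / 0.18² = 54.6, so 55 per group.
- Noncentral t: power is 89.7% at 55 per group and 90.2% at 56. The figure of 56 reproduces.
- Enrollment: 112 / (1 − 0.25) = 149.3, so 150. This reproduces too. The blinding point does not dispute the sample size.

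**5. Illustration: what an assumed bias would do**

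The documents give no estimate of bias; the sizes below are assumptions. Suppose there is no true effect, and let b be a spurious shift in the mean PHIT − UC difference. SE = 0.29 × √(2/56) = 0.0548 m/s. The two-sided rejection rate follows from a noncentral t with 110 df and noncentrality b / SE:

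| Assumed shift b (m/s) | b / SE | Rejection rate |
|---|---|---|
| 0 | 0 | 5.0% |
| 0.02 | 0.365 | 6.5% |
| 0.03 | 0.547 | 8.4% |
| 0.05 | 0.912 | 14.8% |
| 0.10 | 1.825 | 44% |

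If only half of PHIT assessments were affected, the mean shift halves. Individual shifts of 0.02, 0.05 and 0.10 m/s then give 5.4%, 7.4% and 14.8%.

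**6. Scale of a small timing difference**

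Assume a 4-meter course (the pilot's 4MW label in Figure 2), a speed of 0.6 m/s and a 0.3 s change in recorded time; the last two are not in the documents. 4 / 0.6 = 6.667 s; 4 / (6.667 − 0.3) = 0.628 m/s; the change is 0.028 m/s. That is 28% of the 0.1 m/s the plan calls clinically important, and about 16% of the 0.18 m/s it is powered for. It is a shift in one person's result. It becomes a bias of that size in the treatment effect only if it occurs in every PHIT test, in one direction, and in no UC test.

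**The case against.** A reader might infer that blinding rests on nothing but asking participants to keep quiet, and that the assessor can see the allocation. The documents support neither. The plan has several other safeguards, set out above. No sentence places the press or any paper in view at a test visit, and the primary test comes about 30 days after the program should have ended.

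The cues may also be weak. The home exercise activities are the same in both arms apart from intensity. All participants receive some nutrition education at baseline (D2.5), so nutrition material alone need not identify the arm; only the protein handout is specific to PHIT. D2.5 describes a daily walking program for PHIT but mentions no written prescription or log. The handouts are in an appendix, and the test instruments are attached separately; neither is available here. The handouts may look alike, and the gait instructions may already be scripted tightly enough to limit assessor influence.

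All of this stands, and it limits the point to a vulnerability. It does not remove it: no safeguard concerns what is visible, the day-30 visit may overlap with treatment, and without a record of unmasking the sponsor could not later show that blinding held.

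A further objection is to dropping unmasked visits from the analysis. That exclusion depends on an event after randomization that may occur mainly in PHIT and may be related to recovery. The objection is correct, and such a re-analysis cannot replace the primary analysis.

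**Conclusion.** The point holds as a vulnerability in assessor blinding: the assessor may be able to infer the arm, and the plan neither guards against this nor would detect it. That rests on home testing, PHIT-only written material and equipment, and safeguards confined to knowledge and speech. The exercise question at study visits and the conflict over who supervises walking tests strengthen it.

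It is not shown that blinding fails. The size of any bias cannot be estimated from the documents. The illustrative range runs from almost nothing (5.4% rejection if half of PHIT tests shift by 0.02 m/s) to serious (14.8% for a 0.05 m/s shift in the mean difference), entirely by assumption. The case for acting is that the remedy costs little and the primary conclusion depends on one assessor-timed measure.

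**What to change.** Add to Blinding of Research Staff, and align Sections IV.A, IV.C and D2.3 with it:

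1. Before each assessment, a reminder call asks participants in both arms to put away therapy sheets, nutrition material and any equipment. The same wording in both arms avoids creating a new cue.
2. Gait speed is the first test of the visit, and the question about exercises is asked after it.
3. The descriptions of the assessor and of the person supervising tests are reconciled, so that nobody who knows the allocation supervises an outcome test.
4. After the day-60 gait test the assessor records whether the arm became known, and how. The unmasking rate is reported by arm.

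The intent-to-treat primary analysis and the sample size stay as they are. Any re-analysis without unmasked visits is labelled a sensitivity analysis, with the caveat that it excludes participants on a post-randomization event.

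Cost: a longer reminder script (the documents describe no reminder call, so the call itself may be new), one case-report field and a fixed test order. Item 3 may constrain rostering if the research physical therapists now cover test visits; the documents do not say how often they do.

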The **St. Louis University Mental Status Examination (SLUMS)** screens for cognitive impairment by assessing participant function in the areas of attention, calculation, immediate and delayed recall, animal naming, abstract thinking and visuospatial skills.⁶⁴ Patient examination with the SLUMS test is used in both clinical and research settings to screen for dementia. The SLUMS test has strong concurrent validity with the Mini-Mental Status Examination, and is a reliable screening tool for the presence of cognitive impairments with a reported sensitivity of 95-98% and a specificity of 76-100%.⁶⁵

The **Patient Activation Measure (PAM)** identifies patient motivation levels regarding their healthcare. The PAM tool can reliably predict future ER visits, hospital admissions, and medication/ therapy adherence. The survey classifies patient activation levels on a scale from 1 (low activation/motivation) to 4 (high activation/motivation). Patients who score higher on the PAM survey tend to be hospitalized less and adhere to medication and therapy schedules more.

B. Description of Population to be Enrolled:

In this study, the target population is community-dwelling older Veterans or spouses of Veterans, 55 years of age and older, who either were hospitalized or who are medically deconditioned (experienced a decline in physical function) as a result of physical activity restrictions due to COVID-19), have several comorbid conditions, and are eligible for home health physical therapy. These patients will either provided with a COMIRB approved flyer describing the study or will be approached in the hospital and asked if they would agree to participate in a study examining the effects of Usual Care (UC) vs progressive high intensity therapy (PHIT) intervention following hospitalization.

Formal inclusion/exclusion criteria are:

Inclusion Criteria for Veterans/spouse of Veteran (All criteria must be met):

- 1. Veteran status or spouse of Veteran
- 2. 55 years of age and older
- 3. Eligible for home care physical therapy
- 4. Have at least 3 comorbid conditions including those listed below:

| o COPD | Gastrointestinal Bleed | Urinary Tract Infection |
|---|---|---|
| Pneumonia Hypertension Hernia | Chronic ulcerative Depression/mental Post-op pancreatic | Diabetes Irritable Bowel Syndrome Osteoporosis/OA/RA/Gout |

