After patients are consented, they will be randomized to either the PHIT treatment group or UC group using a randomization table that will be prepared by [name] (biostatistician) and held by the home health discharge coordinator at the VA who coordinates all referrals to the home health agency. Randomization assignments will be computer generated using random block sizes of 4 and 6. Randomization will occur via a centralized computer randomization system.

The discharge coordinator will then refer the patient to the home health agency who is delivering the intervention (The Visiting Nurses Association or Berkley Home Health) and inform the agency of the group assignment and ensure that the appropriately trained therapist (UC or PHIT) is scheduled to see the patient. The PRA will then provide the patient contact information to a blinded outcomes assessor (physical therapist or trained research assistant) to complete the baseline evaluation (functional tests and questionnaires). Therapists will be told not to reveal or discuss their assigned protocol to other therapists. [name] has successfully worked with the VNA to train PT staff and implement the proposed investigation for the preliminary data. This protocol has been followed for 22 patients recruited to-date without difficulty, and was successfully implemented, assessed, and the pilot data published.

Caregivers will be approached and, if eligible and willing, consented in the home setting of an enrolled Veteran. A research assistant will explain the study and the goals, and ask eligible caregivers to participate in filling out the caregiver burden inventory after signing a HIPAA waiver. We will only collect and record age (categories by decade) and gender of the caregiver in addition to caregiver burden scores.

D2.4. Interdisciplinary Coordination of Care: Following enrollment, Drs. [name], [name], [name], [name], [name], and Ha will remain involved in the interdisciplinary coordination of patient care as the physician contact following hospital discharge.

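### With spouses eligible and no household rule, two people in one home can be randomised to different arms; the likely effect is small and a one-per-household rule would prevent it

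*Combined protocol and SAP*

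**What the plan says.** **Who may enrol.** Section IV.B states that "the target population is community-dwelling older Veterans or spouses of Veterans, 55 years of age and older". The first inclusion criterion is "Veteran status or spouse of Veteran", so either member of a couple can qualify. D2.2 repeats this, and Sample Size Estimates counts Veterans and spouses together towards the 150 enrolled and 112 completers. Hospitalisation is not required: IV.B also admits people deconditioned "as a result of physical activity restrictions due to COVID-19". D2.3 adds recruitment by clinician flyer, with consent at home.

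**Allocation.** D2.3 says: "After patients are consented, they will be randomized to either the PHIT treatment group or UC group". It adds: "Randomization assignments will be computer generated using random block sizes of 4 and 6". No text limits enrolment to one person per household, keeps a household in one arm or stratifies by household. The exclusion for existing home health physical therapy concerns the patient's own status, not a partner's.

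**Setting.** PHIT is given in 10-12 home visits (D2.5), and outcome testing is also at home (Section II). On nutrition, D2.5 says: "Written education about what foods contain at least 15g of protein will be provided to all PHIT group participants". Both arms receive a home exercise programme with the same activities at different intensity.

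**Caregivers.** The only inclusion criterion is "Primary caregiver for an enrolled participant in the study", and the only exclusion is probation or alternative sentencing. D2.3 limits caregiver data to age by decade, gender and burden scores.

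**Analysis.** Section F regresses 60-day change in gait speed on treatment and baseline gait speed. The sample size rests on a two-group t-test. Neither has a household term.

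**The concern.** The plan takes contamination and unblinding seriously. Each therapist delivers one arm only and is told not to discuss the protocol with other therapists. Agency therapists are not told the study's specific goals. Patients are told not to describe their sessions to the assessor. None of these safeguards deals with two participants who live together.

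In a split household three things could happen:

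- The usual-care member could take up part of PHIT, which would shrink the difference between arms.
- The assessor could see signs of both regimens on one visit.
- If one member is the other's primary caregiver, the Caregiver Burden Inventory score (an Aim 3 outcome) could reflect the caregiver's own treatment. The listed caregiver data items would not show this.

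Separately, members of a couple may have correlated outcomes, whereas the primary regression treats participants as independent.

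**Working it through.** **Inputs from Sample Size Estimates:** difference 0.18 m/s, SD 0.29 m/s, 56 completers per arm, two-sided alpha 0.05, t-test.

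**Assumptions (not in the documents):** the number of couples among completers; f, the share of the PHIT effect that a usual-care partner gains; and rho, the within-couple correlation of 60-day change.

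**1. The plan's own figure.** The standard error is 0.29 × √(2/56) = 0.0548, and 0.18/0.0548 = 3.28. Power is 90.7% by the normal approximation and 90.2% by the exact noncentral t, so the stated 90% reproduces. Enrolment also reproduces: 112/(1 − 0.25) = 149.3, rounded up to 150.

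**2. Chance that a couple is split.** If the two are randomised far apart, it is about 1/2. If they are randomised consecutively, it is 2/3 within a block of 4 and 3/5 within a block of 6. Across a block boundary it is 1/2. With both block sizes equally likely: [(3 × 2/3 + 1/2) + (5 × 3/5 + 1/2)]/10 = 6/10 = 60%.

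**3. Contamination.** With k split couples, the diluted difference is 0.18 × (1 − f × k/56). For k = 2.5 and f = 50%, this is 0.18 × (1 − 1.25/56) = 0.176. Power is by exact t, against a base of 90.2%:

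| Split couples k | f | Difference (m/s) | Power |
|---|---|---|---|
| 2.5 (5 couples, half split) | 10% | 0.179 | 90.0% |
| 2.5 | 25% | 0.178 | 89.6% |
| 2.5 | 50% | 0.176 | 88.9% |
| 2.5 | 100% | 0.172 | 87.5% |
| 5 (10 couples, half split) | 50% | 0.172 | 87.5% |
| 5 | 100% | 0.164 | 84.3% |
| 10 | 100% | 0.148 | 76.2% |

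**4. Independence.** With c same-arm couples and d split couples, the variance of the arm difference is multiplied by 1 + rho × (c − d)/56. The true alpha of the unadjusted test is 2 × [1 − Φ(1.96/√ratio)]. For 10 couples and rho = 0.3:

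- All same arm: 1 + 0.3 × 10/56 = 1.054, alpha 0.056.
- All split: 1 − 0.3 × 10/56 = 0.946, alpha 0.044.
- Half and half: ratio 1.000, alpha 0.050.
- 60% split: 1 + 0.3 × (4 − 6)/56 = 0.989, alpha 0.049.

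Individual randomisation leads to one of the last two cases on average. An extreme case, with 20 couples all in the same arm and rho = 0.5, gives alpha 0.071.

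**5. Blinding and caregiver data.** The documents give no figure from which either effect could be calculated.

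**The case against.** The strongest reply is that the problem may never arise. No text says that a couple has enrolled or is expected to. Each partner must separately have at least three comorbidities, be eligible for home physical therapy, walk at 0.3-1.0 m/s, qualify through hospitalisation or COVID-19 deconditioning, and meet no exclusion. This stands: the harms are possible, not established.

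The second reply is that PHIT is hard to pick up by sharing a home. It is a supervised programme at 8-repetition maximum on a portable press, with load reviewed weekly. Both arms also receive basic nutrition education at baseline. This largely stands. Transfer of 50-100% is only an assumption, and at 10-25% the loss of power is under one percentage point for 2.5 split couples. On the other side, the home programmes share the same exercises, so intensity is the one thing that has to cross over.

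Third, home testing carries some risk of unblinding for every PHIT participant. In a split home, visible equipment would not by itself show which partner is in which arm. This also stands: the documents allow extra exposure but do not show that allocation would be revealed.

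Fourth, the caregiver overlap needs a person who is both deconditioned enough to enrol and the primary caregiver of another participant, and it touches only a secondary outcome. That limits its weight, but the criteria do permit it.

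A reader might go further and infer that household pairs invalidate the primary regression. The working does not support this, because same-arm and split couples roughly cancel. A reader might also infer that the bias always runs towards no difference. That holds for contamination only; unblinding could favour PHIT.

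**Conclusion.** The gap is real. The eligibility and randomisation text permits two members of one household to be allocated to different arms, and no existing safeguard covers it. Spouse eligibility is the most evident route, but two Veterans sharing a home would raise the same issue.

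The probable effect on the primary result is small. It is a loss of about 1 to 3 percentage points of power with 5 couples, half of them split, and 50-100% transfer, and less with lower transfer. A serious loss needs something like 10 split couples with full transfer. The effect on type I error is negligible under individual randomisation. All these sizes depend on assumed numbers of couples and assumed transfer, and they use the plan's unadjusted t-test, not its baseline-adjusted model. The blinding and caregiver effects cannot be sized.

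This is a low-priority improvement. It is worth making because analysts cannot remove contamination or unblinding once they have happened.

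**What to change.** Add two sentences to the eligibility criteria in IV.B and D2.2:

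- Only one member of a household may be randomised. This also covers two Veterans who live together.
- A randomised participant may not also supply caregiver-burden data.

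For household pairs already enrolled, report their number and arms, including a count of zero. Keep them in the intent-to-treat analysis and add two sensitivity analyses of the primary outcome:

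- One with household-clustered standard errors, which deals with correlation.
- One that excludes split households, which deals with contamination. For a split pair this removes one person from each arm. Keeping only the first-enrolled member would not be enough, because a retained usual-care partner would still have been exposed.

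The sample size need not change: 112 completers, 150 enrolled. The cost is that a few second household members are not enrolled and a few caregiver scores are lost.
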